5.4 Overdose

There are currently no specific treatments in the event of overdose with acalabrutinib, umbralisib or ublituximab and possible symptoms of overdose are not established. In the event of an overdose, the participant should be monitored as clinically appropriate (e.g. vital signs, hematologic parameters, etc.) and adverse reactions associated with the overdose should be treated symptomatically. Please refer to **Section 7.4** for adverse event reporting requirements.

In the event of an overdose ingestion of acalabrutinib that is recent and substantial, and if there are no medical contraindications, use of gastric lavage or induction of emesis may be considered at the treating investigator's discretion and in accordance with local institutional guidelines.

5.5 Withdrawal of Umbralisib and Ublituximab

As of March 2023, TG therapeutics has decided to no longer provide umbralisib, ublituximab and funding for this study. Study participants still on treatment will still have the option to continue taking acalabrutinib.

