12. STATISTICAL CONSIDERATIONS

12.1 Study Design

An open label, non-randomized phase 2 trial assessing the combination of acalabrutinib, umbralisib, and ublituximab in adult participants with chronic lymphocytic leukemia (CLL). Participants will be enrolled to one of two treatment cohorts:

- **Cohort 1:** Participants with relapsed disease
- **Cohort 2:** Participants who are treatment naïve

Each cohort will follow a one-stage enrollment design, accruing a maximum of 30 participants.

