12.2 Sample Size, Accrual Rate and Study Duration

A total of 30 participants will be accrued to each cohort, for a maximum total of 60 participants. The anticipated overall accrual rate is approximately 4 patients per month, for a planned accrual duration of about 15 months. Participants will receive treatment for 24 cycles (2 years) and will continue to be followed for a maximum of 5 years following treatment discontinuation for survival, for a total study length of approximately 8 years.

Table 25: Accrual Targets					
Ethnic Category	Sex/Gender				
	Females		Males		Total
Hispanic or Latino	1	+	3	=	4
Not Hispanic or Latino	20	+	36	=	56
Ethnic Category: Total of all subjects	21	(A1)	+ 39	(B1) =	60 (C1)
Racial Category					
American Indian or Alaskan Native	0	+	0	=	0
Asian	1	+	1	=	2
Black or African American	1	+	3	=	4
Native Hawaiian or other Pacific Islander	0	+	0	=	0
White	19	+	35	=	54
Racial Category: Total of all subjects	21	(A2)	+ 39	(B2) =	60 (C2)
	(A1 = A2)		(B1 = B2)		(C1 = C2)

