12.4 Analysis of Primary Endpoints

The primary endpoint is the rate of CR after 24 cycles of treatment with acalabrutinib, umbralisib, and ublituximab in previously untreated and relapsed CLL patients, assessed per 2018 IW-CLL criteria.¹

Nastoupil et al. reported a CR rate of 44% in previously treated CLL participants who received ibrutinib, umbralisib, and ublituximab.¹⁶ We hypothesize the CR rate will be 44% in **Cohort 1**; given that the depth of response for treatment naïve disease will likely be greater, we hypothesize a CR rate of 50% in **Cohort 2**.

For **Cohort 1**, if 10 or more patients achieve CR by the completion of 24 cycles, we will regard the treatment as efficacious. This sample size provides an $\alpha=0.06$ (false positive type I error) and power $\beta = 91\%$ (one minus false negative type II error) using a one-sided one sample binomial test comparing to a null hypothesis of 20% complete response rate with one BCR inhibitor plus an antibody.

For **Cohort 2**, if 13 or more patients achieve CR by the completion of 24 cycles, we will regard the treatment as efficacious. This sample size provides an $\alpha=0.08$ (false positive type I error) and power $\beta = 82\%$ (one minus false negative type II error) using a one-sided one sample binomial test comparing to a null hypothesis of 30% response rate for one BCR inhibitor plus an antibody.

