12.6.2 Evaluation of the Primary Efficacy Endpoint

All participants who receive at least one dose of at least one of the study agents will be considered evaluable for the primary efficacy endpoint in an intent-to-treat analysis.

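### Does the March 2023 withdrawal of two of the three study drugs oblige the sponsor to rewrite the analysis in Section 12?

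*Combined protocol and SAP*

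**What the plan says.** Section 5.5 dates the decision to March 2023: "TG therapeutics has decided to no longer provide umbralisib, ublituximab and funding for this study". It then adds: "Study participants still on treatment will still have the option to continue taking acalabrutinib".

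Section 12 is written for the full regimen.

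- **Endpoint (12.4):** "the rate of CR after 24 cycles of treatment with acalabrutinib, umbralisib, and ublituximab".
- **Success rule (12.4):** treatment is regarded as efficacious in Cohort 1 "if 10 or more patients achieve CR by the completion of 24 cycles", with alpha 0.06 and power 91% (null 20%, hypothesised rate 44%). In Cohort 2 it is so regarded "if 13 or more patients achieve CR by the completion of 24 cycles", with alpha 0.08 and power 82% (null 30%, hypothesised rate 50%). Both use a one-sided one-sample binomial test.
- **Size:** 12.1 describes a one-stage design "accruing a maximum of 30 participants", and 12.2 states "A total of 30 participants will be accrued to each cohort".
- **Analysis set (12.6.2):** evaluable for the primary endpoint are "All participants who receive at least one dose of at least one of the study agents", by intention to treat. Section 12.6 excludes only those who never start therapy.
- **Discontinuation (12.5):** a descriptive analysis up to cycle 12, which includes loss of individual components. The reasons listed are examples.

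Under Section 4.1, ublituximab is given only in cycles 7 to 12. Participants in confirmed CR at the end of cycle 12 stop both oral drugs, and the others continue into cycles 13 to 24.

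**The concern.** The protocol was amended for conduct, but its statistical section was not. Two things seem to be left open.

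First, a participant not in CR at cycle 12 is due to take umbralisib until cycle 24. If supply ended during those cycles, the loss falls outside the 12.5 summary. The objective in Section 1.3 on early discontinuation sets no cycle limit.

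Second, loss of drug and funding is the kind of event that closes a cohort early. The counts of 10 and 13 were fixed for 30 participants, 12.1 makes 30 a ceiling, and no rule covers a smaller cohort. Literal use of the counts could then miss a real effect.

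There is also a risk of an improvised repair. Only participants not in CR enter cycles 13 to 24, so dropping those who lost umbralisib there would remove non-responders and raise the CR rate.

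**Working it through.** **1. Reproduce the plan's figures.** Inputs from 12.4: n = 30; r = 10, p0 = 0.20, p1 = 0.44 (Cohort 1); r = 13, p0 = 0.30, p1 = 0.50 (Cohort 2). With X binomial,

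P(X ≥ r | n, p) = Σ_{k=r}^{n} C(n,k) p^k (1−p)^{n−k}.

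- Cohort 1: P(X ≥ 10 | 30, 0.20) = 0.0611; P(X ≥ 10 | 30, 0.44) = 0.9148.
- Cohort 2: P(X ≥ 13 | 30, 0.30) = 0.0845; P(X ≥ 13 | 30, 0.50) = 0.8192.

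All four agree with the plan at the precision it prints.

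**2. Hold the counts and lower n.** The smaller sizes are assumptions; the documents give no achieved enrolment.

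| n | Cohort 1 alpha / power | Cohort 2 alpha / power |
|---|---|---|
| 30 | 0.0611 / 91.5% | 0.0845 / 81.9% |
| 29 | 0.0493 / 89.0% | 0.0652 / 77.1% |
| 28 | 0.0391 / 85.9% | 0.0491 / 71.4% |
| 25 | 0.0173 / 72.5% | 0.0175 / 50.0% |
| 20 | 0.0026 / 37.4% | 0.0013 / 13.2% |

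Power falls, and so does alpha. A short cohort cannot raise the false-positive rate under the written rule.

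**3. Does the plan leave the analyst stuck at a smaller n?** No. The test, its direction and both null rates are stated, so the exact p-value follows at any n. For example, at an assumed n = 25, 9 remissions in Cohort 1 give P(X ≥ 9 | 25, 0.20) = 0.0468, and 12 in Cohort 2 give P(X ≥ 12 | 25, 0.30) = 0.0442. Both can be set beside the design alphas of 0.0611 and 0.0845.

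**4. Effect of lost drug with n kept at 30.** Suppose 5 of 30 participants were cut short before cycle 13 and responded at the null rate, or at the roughly 10% that Section 2.1 gives for targeted agents. Adding Bin(25, p1) and Bin(5, q) gives power of 82.8% or 78.0% in Cohort 1, and 70.9% or 57.5% in Cohort 2. With those 5 at 10% and the other 25 at the null rate, alpha is 0.035 and 0.034. Again the error is conservative. Nothing in the documents shows that this number is above zero. The illustration does not carry over to cycles 13 to 24, where those affected are already known not to be in CR.

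**5. The exclusion risk.** Taking 10 remissions in 30 as an example, the rate is 10/30 = 33%; dropping 5 non-responders makes it 10/25 = 40%. If all remissions occur by cycle 12, testing at the n = 25 counts after such exclusions has a false-positive rate of P(X ≥ 9 | 30, 0.20) = 0.129 and P(X ≥ 12 | 30, 0.30) = 0.159. That would matter, but 12.6.2 rules it out.

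**6. Are the exposure data there?** Table 23 in Section 9 schedules umbralisib data entry on Day 1 of cycles 13 to 24. Section 4.5 requires the reason and date of removal from protocol therapy on the case report form. Someone who loses umbralisib but stays on acalabrutinib may not count as removed, yet the umbralisib entries and the date in Section 5.5 identify that case. Supply loss also fits among the open-ended reasons in 12.5.

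**The case for a change.** The best argument for acting is that the sponsor knows its own enrolment and treatment status, the wording would cost little, and a rule written beforehand is better than one chosen afterwards. The cycle 13 to 24 gap also does not depend on enrolment: with full cohorts, anyone still taking umbralisib in those cycles at withdrawal falls outside the planned summary. Both observations on the text are correct.

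The remedies on offer add little, and some carry a cost.

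- **Reduced success counts.** Lowering the counts for short cohorts, in an open-label single-arm trial and after March 2023, relaxes the bar when responses may already be visible. It would also answer an event that no section reports. The gain in power at an assumed n = 25 (72.5% to 84.3% with 9 remissions, 50.0% to 65.5% with 12) is real only if a cohort closed that short.
- **Split by first-dose date.** This needs a last-supply date. Section 5.5 dates a decision, not the final dispensing. Late starters already in CR at cycle 12, who need no further oral drug, would be counted as affected.
- **Longer component table.** This is useful description, but it does not alter the primary conclusion. Reading early discontinuation as discontinuation by cycle 12 is a fair interpretation of Section 1.3.

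**Conclusion.** No change to the plan is needed. Section 12 does not mention the withdrawal, and 12.5 stops at cycle 12, but these are gaps that an analyst fills sensibly from what is already written: the intent-to-treat set in 12.6.2, the named test and null rates in 12.4, and the dosing and removal records. Reporting the withdrawal, showing umbralisib stops through cycle 24 and, if a cohort fell short, giving the exact p-value and power at the achieved size is ordinary practice under this plan.

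The size of any effect cannot be stated. At 30 per cohort the success rule behaves as printed. Below 30 it loses power (to 85.9% and 71.4% at 28, for instance) without raising the false-positive rate. This conclusion rests on two conditions: the documents show no cohort closed below 30, and 12.6.2 is followed, so that nobody is dropped for losing a drug. The step 4 figures also assume that losing a component does not raise the chance of CR.

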6. ADVERSE EVENTS: LIST AND REPORTING REQUIREMENTS

Adverse event (AE) monitoring and reporting is a routine part of every clinical trial. The following list of reported and/or potential AEs (**Section 7.1**) and the characteristics of an observed AE (**Sections 7.2, 7.3, 7.4 and 7.5**) will determine whether the event requires expedited reporting **in addition** to routine reporting.

6.1 Expected Toxicities

6.1.1 Expected Toxicities for Acalabrutinib

For the purposes of suspected unexpected serious adverse reaction (SUSAR) reporting, the toxicities in the table below will be considered expected for acalabrutinib. Events that are fatal or life-threatening (i.e. posing an immediate risk of dying) must always be reported according to expedited timelines. Please also refer to the acalabrutinib IB.

Table 13: Acalabrutinib Expected Toxicities	
System Organ Class	Event
Gastrointestinal disorders	Abdominal pain
	Diarrhea
	Vomiting
Nervous system disorders	Headache
Vascular disorders	Hematoma

6.1.2 Expected Toxicities for Umbralisib

For the purposes of SUSAR reporting, the toxicities in the table below will be considered expected for umbralisib. Events that are fatal or life-threatening (i.e. posing an immediate risk of dying) must always be reported according to expedited timelines. Please also refer to the umbralisib IB.

Table 14: Umbralisib Expected Toxicities

System Organ Class	Event	Frequency (n=number of occurrences)	Serious
Blood and Lymphatic System Disorders	Febrile Neutropenia	8	Yes
	Anemia	4	Yes
	Neutropenia	2	Yes
	Thrombocytopenia*		
	Leukopenia*		
	Leukocytosis*		
Cardiac Disorders	Cardiac Failure	2	Yes
	Congestive		
	Heart Palpitations	1	Yes
	Pulmonary Edema	1	Yes
Congenital, Familial and Genetic Disorders	Congestive Heart Failure	1	Yes
Gastrointestinal Disorders	Diarrhea	9	Yes
	Small Intestinal Obstruction	2	Yes
	Nausea	2	Yes
	Vomiting	2	Yes
	Colitis	3	Yes
	Anorectal Fistula	1	Yes
	Acute Pancreatitis	1	Yes
	Ileus	1	Yes
	Abdominal Pain*		
	Gastrointestinal Hemorrhage*		
General Disorders and Administrative Site Conditions	Pyrexia	6	Yes
	Fatigue	3	Yes
	Pyrexia*		
Immune System Disorders	Uveitis	1	Yes
	Allergic Reaction	1	Yes
Infections and Infestations	Pneumonia	18	Yes
	Cellulitis	3*	Yes
	Cytomegalovirus Colitis	2	Yes
	Lung Infection	2	Yes

Table 14: Umbralisib Expected Toxicities

System Organ Class	Event	Frequency (n=number of occurrences)	Serious
	Sepsis	12	Yes
	Septic Shock	1	Yes
	Upper Respiratory Tract Infection	2	Yes
	Neutropenic Sepsis	2	Yes
	Bacteremia	2	Yes
	Pulmonary Infection		
Investigations	Transaminases Increased	2	Yes
	Elevated Liver Enzymes*		
Metabolism & Nutrition Disorders	Dehydration	5	Yes
	Hypophosphatemia	2	Yes
	Tumor Lysis Syndrome*	2	Yes
Nervous System Disorders	Headache	3	Yes
	Syncope	2	Yes
	PML*	1	Yes
Neoplasms Benign, Malignant and Unspecified (incl cysts and polyps)	Malignant Melanoma*	1	Yes
Respiratory, Thoracic and Mediastinal Disorders	Pneumonitis	4	Yes
	Pleural Effusion	2	Yes
	Hypoxia	2	Yes
	Shortness of Breath*		
Skin and Subcutaneous Tissue Disorders	Rash	4	Yes
	Eczema	2	Yes
	Erythrodermic Eczematous Rash*	1	Yes
*: these events have not been seen as a serious adverse reaction ≥ 2 however are still considered to be of special interest for umbralisib			

6.1.3 Expected Toxicities for Ublituximab

For the purposes of SUSAR reporting, the toxicities in the table below will be considered expected for ublituximab. Events that are fatal or life-threatening (i.e. posing an immediate risk of dying) must always be reported within expedited timelines. Please also refer to the ublituximab IB.

Table 15: Ublituximab Expected Toxicities

System Organ Class	Event	Frequency (n=number of occurrences)	Serious
Blood and Lymphatic System Disorders	Febrile Neutropenia	8	Yes
	Anemia	2	Yes
	Thrombocytopenia	2	Yes
	Pancytopenia*		
Gastrointestinal Disorders	Diarrhea	3	Yes
General Disorders and Administrative Site Conditions	Pyrexia	5	Yes
	Fatigue	3	Yes
Immune System Disorders	Serum Sickness-Like Reaction	1	Yes
	Hypersensitivity/Anaphylaxis*		
Infections and Infestations	Pneumonia	14	Yes
	Sepsis	6	Yes
	Neutropenic Sepsis	2	Yes
	Cellulitis	2	Yes
	Bacteremia	2	Yes
	Septic Shock	2	Yes
Injury, Poisoning and Procedural Complications	Infusion-Related Reactions	9	Yes
Metabolism & Nutrition Disorders	Hypercalcemia	1	Yes
	Insulin Dependent Diabetes	1	Yes
	Tumor Lysis Syndrome	4	Yes
Nervous System Disorders	PML	1	Yes
Neoplasms Benign, Malignant and Unspecified (incl cysts and polyps)	Malignant Melanoma	1	Yes
Skin and Subcutaneous Tissue Disorders	Rash	3	Yes
	Erythrodermic Eczematous Rash	2	Yes

*: these events have not been seen as a serious adverse reaction ≥ 2 however are still considered to be of special interest for ublituximab

6.2 Adverse Event Characteristics

- **Term (AE description) and grade:** The descriptions and grading scales found in the revised NCI Common Terminology Criteria for Adverse Events (CTCAE) version 5.0 will be utilized for AE reporting for non-hematologic toxicity. All appropriate treatment areas should have access to a copy of the CTCAE version 5.0. A copy of the CTCAE version 5.0 can be downloaded from the CTEP web site http://ctep.cancer.gov/protocolDevelopment/electronic_applications/ctc.htm. The iwCLL 2018 criteria will be used for grading and assessment of hematologic toxicity (**Appendix E**).¹
- **For expedited reporting purposes only:**
 - AEs for the agent(s) that are listed above should be reported only if the adverse event varies in nature, intensity or frequency from the expected toxicity information which is provided.
 - Other AEs for the protocol that do not require expedited reporting are outlined in the next section (Expedited Adverse Event Reporting) under the sub-heading of Protocol-Specific Expedited Adverse Event Reporting Exclusions.
- **Attribution of the AE:**
 - Definite – The AE is *clearly related* to the study treatment.
 - Probable – The AE is *likely related* to the study treatment.
 - Possible – The AE *may be related* to the study treatment.
 - Unlikely – The AE is *doubtfully related* to the study treatment.
 - Unrelated – The AE is *clearly NOT related* to the study treatment.

6.3 Serious Adverse Event Reporting

A serious adverse event (SAE) is any adverse event that occurs after the initial dose of study treatment, during treatment, or within 30 days of the last dose of treatment that results in one of the following outcomes or meets at least one of the following criteria:

- Death
- Hospitalization for greater than 24 hours
- Prolonging an existing inpatient hospitalization
- A life-threatening experience (that is, immediate risk of dying)
- Persistent or significant disability/incapacity
- Congenital anomaly/birth defect
- Any suspected transmission of an infectious agent via a study agent (e.g. Prion Protein Transmitting Transmissible Spongiform Encephalopathy)
- Any confirmed occurrence of Hy's Law, defined as an ALT or AST $\geq 3 \times$ institutional ULN **AND** concurrent total bilirubin $\geq 2 \times$ institutional ULN without findings of cholestasis
- Considered significant by the investigator for any other reason

If an investigator becomes aware of an SAE that is considered related to acalabrutinib after completion of the 30-day period following the last dose of acalabrutinib, the event should also be reported as an SAE to Acerta Pharma at the contact information given below.

Previously planned (prior to signing the informed consent form) surgeries, and non-disease related elective surgeries planned during the course of the study, should not be reported as SAEs unless the underlying medical condition has worsened or appeared during the course of the study. Events that occur prior to the first administration of study medication should not be reported as SAEs.

Preplanned hospitalizations or procedures for pre-existing conditions that are already recorded in the patient's medical history at the time of study enrollment should not be considered SAEs. Hospitalization or prolongation of hospitalization without a precipitating clinical AE (e.g., for the administration of study therapy or other protocol-required procedure) should not be considered SAEs.

Important medical events that may not result in death, be life-threatening, or require hospitalization may be considered SAEs when, based on appropriate medical judgment, they may jeopardize the patient and may require medical or surgical intervention to prevent one of the outcomes listed in this definition.

Death due to disease progression should not be reported as an SAE unless the investigator deems it to be related to the use of study drug. Hospitalization due solely to the progression of underlying malignancy should NOT be reported as an SAE. Clinical symptoms of progression may be reported as SAEs if the symptoms cannot be determined as exclusively due to the progression of the underlying malignancy, or if they do not fit the expected pattern of progression for the disease under study. If there is any uncertainty about an SAE being due only to the disease under study, it should be reported as an SAE.

Study site personnel must alert the sponsor-investigator of any SAE as soon as possible and no later than 1 business day of the treating investigator receiving notification of the SAE experienced by a patient participating in the study. Study site personnel must alert TG Therapeutics, Inc. of any SAE within 24 hours of the first knowledge of the event by the treating physician or research personnel. Study site personnel must alert Acerta Pharma within 15 calendar days of awareness of any SAEs. The SAE reports should be on a standard reporting form (e.g. CIOMS, local institutional SAE form, MedWatch 3500a, or similar) and are to be sent via email to TG Therapeutics, Inc.: [contact] and Acerta Pharma: [contact].

6.4 Adverse Events of Special Interest (AESI)

6.4.1 Pregnancy

During the course of the study, all female participants of childbearing potential must contact the treating investigator immediately if they suspect that they may be pregnant (a missed or late menstrual period should be reported to the treating investigator). If an investigator suspects that a participant may be pregnant, the study drugs must be withheld until a pregnancy test has been administered and the result has been confirmed. If a pregnancy is confirmed, the patient must be permanently discontinued from the study treatment. The investigator should counsel the subject, discussing any risks of continuing the pregnancy and any possible effects on the fetus.

Any pregnancy that occurs with the subject or with the partner of a treated subject during the study intervention period, or that occurs within 30 days following the last dose of study medication, will be reported, followed to conclusion, and the outcome reported. Abortions (spontaneous, accidental, or therapeutic) must also be reported.

Study site personnel must alert the sponsor-investigator and submit an SAE form (CIOMS, local institutional SAE form, or similar) within 15 calendar days to Acerta Pharma at [contact].

Confirmed pregnancies, subject's partner pregnancies, and abortions (spontaneous, accidental, or therapeutic) must be reported to TG Therapeutics, Inc. at [contact] within 24 hours of the first knowledge of the event by the treating physician or research personnel on a Pregnancy Report Form. For subject's partner pregnancies, the partner will be requested to consent to access to medical records. After the subject's partner provides consent, the pregnant partner and baby will be followed to see what effect the drug(s) under study may have on the outcome of the pregnancy or the health of the newborn.

Congenital anomalies/birth defects **always** meet SAE criteria and should therefore be expeditiously reported as an SAE to TG Therapeutics, Inc. at [contact] within 24 hours of the first knowledge of the event by the treating physician or research personnel.

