- 2.7.10 The effects of umbralisib, acalabrutinib, or ublituximab on the developing human fetus are unknown. For this reason and because anti-cancer agents are known to be teratogenic, women of child-bearing potential and men must agree to use highly effective methods of contraception (see **Section 5.4**). Should a woman become pregnant or suspect she is pregnant while she or her partner is participating in this study, she should inform her treating physician immediately. Men and women treated on this protocol must agree to use highly effective contraception prior to the study, for the duration of study participation, and 4 months after completion of umbralisib, acalabrutinib, or ublituximab administration.
- 2.7.11 Ability to understand and the willingness to sign a written informed consent document.
- 2.7.12 Ability to swallow and retain oral medication.
- 2.7.13 Participants must be able to receive prophylactic anti-pneumocystis jiroveci pneumonia (PJP) and anti-viral therapy, see **Section 5.4**.

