4.4.5.2 Fertile Males

Fertile males, defined as all males physiologically capable of conceiving offspring, must use a condom during treatment and for 4 months after the last dose of study treatment. They should also not father a child during this period.

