4.4.5.3 Pregnancies

To ensure patient safety, each pregnancy in a patient on study treatment must be reported and followed as per the guidelines in **Section 7**.

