6.5 Adverse Event Reporting

- 6.5.1 In the event of an unanticipated problem or life-threatening complications treating investigators must immediately notify the PI.
- 6.5.2 Investigators **must** report to the PI any serious adverse event (SAE) or adverse event of special interest (AESI) that occurs after the initial dose of study treatment, during treatment, or within 30 days of the last dose of treatment on the local institutional SAE form.

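### Contraception is required for 4 months after the last dose, but the duty to report and follow a pregnancy ends at 30 days, leaving about 90 of roughly 120 post-dose days without a clear, systematic duty

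*Combined protocol and SAP*

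**What the plan says.** Criterion 2.7.10 (section 2.7, Eligibility Criteria) states that effects on the human fetus are not known and gives its reason for requiring contraception: "For this reason and because anti-cancer agents are known to be teratogenic". Men and women must use it before the study, "for the duration of study participation, and 4 months after completion of umbralisib, acalabrutinib, or ublituximab administration". Section 4.4.5.2 repeats the period for fertile males, who "must use a condom during treatment and for 4 months after the last dose of study treatment" and are told not to father a child in that time.

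The reporting rules use a shorter period:

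- Section 6.4.1 covers a pregnancy in a participant or partner that arises during the intervention period "or that occurs within 30 days following the last dose of study medication, will be reported, followed to conclusion, and the outcome reported".
- Section 6.5.2 has investigators report to the PI each SAE, and likewise any "adverse event of special interest (AESI) that occurs after the initial dose of study treatment, during treatment, or within 30 days of the last dose". Pregnancy is listed under AESIs, as 6.4.1.
- Section 6.3 defines an SAE, including a congenital anomaly, as an event up to 30 days after the last dose.
- Section 4.6 ends adverse event follow-up 30 days after removal from therapy, apart from following unresolved events that caused the removal.
- Section 4.4.5.3 says "each pregnancy in a patient on study treatment must be reported and followed as per the guidelines". It concerns patients on treatment and adds no period afterwards.

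**The concern.** The protocol sets a period after dosing in which it wants no conception, because the fetal effects of the three agents are unknown. It then sets a rule for collecting pregnancies that ends well before that period does. A participant or partner who conceives between day 31 and month 4 is inside the contraception period but outside the rule that requires the pregnancy to be reported and followed to its outcome.

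What is at stake is safety information. With few pregnancies expected, each one carries much of what the trial could learn about exposure. Treatment is also time-limited: participants in CR stop after cycle 12 and the rest after cycle 24. Passing through these four months off drug is therefore a planned part of the design.

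**Working it through.** The plan states no figure to reproduce. The check compares two intervals and then looks for any provision that closes the difference.

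**Inputs.** Contraception after last dose: 4 months (2.7.10, 4.4.5.2). Reporting after last dose: 30 days (6.4.1). Cycle length: 28 days (4.1). Month length is not given, so I varied it from 28 to 30.75 days. I date a pregnancy by conception, which 6.4.1 does not specify.

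**Share of the post-dose window not covered** = (4m − 30) / 4m, with m the days in a month:

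| m | 4m | Not covered (days) | Share |
|---|---|---|---|
| 28 | 112 | 82 | 73% |
| 30 | 120 | 90 | 75% |
| 30.4375 | 121.75 | 91.75 | 75% |
| 30.75 | 123 | 93 | 76% |

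**Share of treatment plus the post-dose window** = (4m − 30) / (28c + 4m), with c cycles and m = 30:

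- 12 cycles: 90 / (336 + 120) = 90/456 = 20%
- 24 cycles: 90 / (672 + 120) = 90/792 = 11%
- 36 cycles (with re-treatment): 90 / (1008 + 120) = 90/1128 = 8%

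**Does anything else cover day 31 to month 4?**

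- The 6.4.1 sentence on alerting the sponsor-investigator and the acalabrutinib supplier names no event of its own. It takes its scope from the preceding paragraph, which contains the 30-day limit.
- The 6.4.1 sentences on the umbralisib/ublituximab supplier cover confirmed pregnancies in participants and partners, abortions and birth defects. They run from first knowledge and state no occurrence window. They reach one supplier only and create no duty to ask.
- Section 6.3 has a route after day 30, but only for an SAE that the investigator learns of and considers related to acalabrutinib. An uneventful pregnancy does not meet the SAE list.
- The 3-monthly long-term contacts in Tables 20, 22 and 23 are there to confirm survival and disease response. Pregnancy is not listed.
- Table 21 schedules adverse event evaluation at all visits for participants off drug in CR. Pregnancy is not named there either.

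**Can existing contacts cover the window?** For participants who stop in CR after cycle 12, cycle 15 day 1 falls 2 × 28 = 56 days after the end of cycle 12, and cycle 18 day 1 falls 5 × 28 = 140 days after. With the 3-day visit window, the latter is at least 137 days, beyond the longest 4-month figure of 123. For the others, contacts at about 3 and 6 months look back over the whole period.

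**The case against.** The strongest reply is that the protocol is not silent after day 30. The supplier sentences in 6.4.1 have no time limit, and birth defects are there said always to be SAEs, which is hard to read as restricted to 30 days. Women of childbearing potential must contact the investigator at once if they suspect pregnancy during the study, and participants stay on study for up to 5 years of follow-up. An acalabrutinib-related SAE has a late route. Participants off drug in CR have visits with adverse event evaluation.

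This stands as far as it goes. A reader might infer from the 30-day sentence that late pregnancies and birth defects would reach nobody, and the documents do not support that. But none of these provisions requires that a pregnancy beginning between day 31 and month 4 be reported to the sponsor-investigator and both suppliers and then followed. The instruction to women does not extend the reporting rule, and it does not reach the partners of male participants. If the supplier sentences are read as unlimited, they sit uneasily with the 30-day sentence in the same section, which is itself a reason to reconcile the text.

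It is also fair that numbers will be small. Section 2.1 puts most patients above 70 at diagnosis and above 75 at first treatment. Table 25 plans 39 men among 60 participants, and a reader might take all 39 as at risk. Section 4.4.5.2 covers only males physiologically able to father a child, and the documents do not say how many that would be. Eligibility does start at age 18, so the number at risk cannot be assumed to be zero.

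**Conclusion.** The mismatch is real and unexplained. About 90 of roughly 120 days after the last dose, 73% to 76% across the month lengths tried, have no clear, systematic duty to report and follow a new pregnancy. A reader might take this as three quarters of all at-risk time. It is not: measured over treatment plus the 4 months, the gap is about 8% to 20%.

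The result rests on dating a pregnancy by conception and on reading the supplier sentences in 6.4.1 as the reporting route for the 30-day rule, or at most as a partial exception to it. The expected number of events is small, though the documents give no figure. The primary endpoint, error rates, power and sample size are untouched. This is a safety-reporting gap that should be closed. Which duration is clinically right is not judged here; the point is that the sections disagree and must be reconciled.

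**What to change.** Reconcile 2.7.10, 4.4.5.2, 4.4.5.3, 6.3, 6.4.1 and 6.5.2:

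- In 6.4.1, define the reporting window by reference to the post-treatment contraception period in 2.7.10 and 4.4.5.2 instead of a separate number of days, so that the two cannot diverge. State that a pregnancy is dated by conception.
- In 6.3 and 6.5.2, state that pregnancy and any resulting congenital anomaly follow this window, with reports to the sponsor-investigator and both suppliers. Make clear that a birth defect found after the window, from a pregnancy that began inside it, is still reported.
- Ask about pregnancy, including in partners, at the 3-monthly long-term contacts (Tables 20, 22, 23) and at the cycle 15 and 18 visits for participants off drug in CR (Table 21).

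The cost is a short amendment, one question at contacts already scheduled, and a few extra reports. Section 15 requires the umbralisib/ublituximab supplier to approve amendments, and section 5.5 records that this supplier has withdrawn drug and funding, so approval may take some arranging. No dose, contraception or treatment rule changes.
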